7.1 DEMOGRAPHIC AND OTHER BASELINE CHARACTERISTICS

Only descriptive statistics are planned for this section.

Descriptive statistics for demographic parameters and baseline characteristics will be presented by treatment, based on the RS.

For the continuous variables described below, categories are defined in Table 7.1:1. These variables will be presented according to the number and percentage of patients in each category, in addition to the display of the summary statistics for continuous variables.

Page 21 of 33

c43185880-01

Proprietary confidential information © 2024 Boehringer Ingelheim International GmbH or one or more of its affiliated companies.

Variable	Categories
Age	< 50
(years)	50 to < 65
	65 to < 75
	≥ 75
	< 65
	≥ 65
Weight	≤ 70
(kg)	$> 70 \text{ to} \le 80$
	$> 80 \text{ to} \le 90$
	> 90
BMI	< 25
(kg/m^2)	25 to < 30
	\geq 30
eGFR	≤ 30
(mL/min/1.73 m ²)	$> 30 \text{ to} \le 45$
	$> 45 \text{ to} \le 60$
	$> 60 \text{ to} \le 90$
	> 90
Time since first diagnosis of	≤1
(years)	> 1 to ≤ 5
	$> 5 \text{ to} \le 10$
	> 10
Baseline HVPG	≤ 12
	> 12
	≤ 15
	> 15

Table 7.1: 1 Categories for summary of continuous variables

7.2 CONCOMITANT DISEASES AND MEDICATION

Only descriptive statistics are planned for this section of the report. Analyses of the concomitant diseases and medication as well as non-drug therapies will be based on RS.

Concomitant diseases will be coded according to the most recent version of Medical Dictionary for Drug Regulatory Activities (MedDRA).

Concomitant medication will be coded according to the most recent version of the World Health Organisation – Drug Dictionary (WHO-DD).

Proprietary confidential information © 2024 Boehringer Ingelheim International GmbH or one or more of its affiliated companies.

A medication/non-drug therapy will be considered concomitant to treatment if it:

- is ongoing at the start of trial medication intake
- starts within the on-treatment period (see Table 6.1:1 for a definition of study analysis phases).

Concomitant medication use will be summarised with frequency and percentage of patients by Anatomical Therapeutic Chemical 3 (ATC3) class and preferred name.

7.3 TREATMENT COMPLIANCE

Only descriptive statistics are planned for this section of the report.

The compliance based on TS will be described as collected in the eCRF. Number and percentage of patients with compliance in following categories will be displayed at each visit since week 1 (visit 3):

- "Yes",
- "No", and
- "Missing".

7.4 PRIMARY OBJECTIVE ANALYSIS

7.4.1 Main analysis

As described in Section 4, planned analysis around HVPG data in the CTP, including primary object analysis, will not be performed.

7.4.4 Supplementary analysis

No supplementary analyses are planned.

7.5 SECONDARY OBJECTIVE ANALYSIS

7.5.1 Key secondary objective analysis

This section is not applicable as no key secondary endpoint has been specified in the protocol.

Proprietary confidential information © 2024 Boehringer Ingelheim International GmbH or one or more of its affiliated companies.

7.5.2 Secondary objective analysis

7.5.2.1 Main analysis

The secondary endpoints for this study are described in CTP Section 2.1.3 and only descriptive statistics will be presented.

For the occurrence of decompensation events, categories are defined in Table 7.5.2:1.

T 11 7 7 0 1	α ·	C 1	1	
Table $7.5.2:1$	Categories	tor c	lecompensation e	vents
	( 7			

Categories	Scope	Definition
Acites		PT - 'Ascites' PT - 'Bacterascites' PT - 'Haemorrhagic ascites'
Variceal haemorrhage	Narrow Narrow Narrow	PT - 'Oesophageal varices haemorrhage' PT - 'Oesophageal haemorrhage' PT 'Bleeding varicose vein'
	Broad Broad	HLT – 'Gastric and oesophageal haemorrhages' HLT – 'Non-site specific gastrointestinal haemorrhages'
Hepatic encephalopathy	Narrow Narrow	PT - 'Hepatic encephalopathy' PT - 'Coma hepatic'
	Broad Broad	PT - 'Hyperammonaemic encephalopathy' PT - 'Hyperammonaemic crisis'
Other		PT - 'Cardiohepatic syndrome' PT - 'Hepatorenal syndrome' PT - 'Hepatorenal failure' PT - 'Hepatic hydrothorax' PT - 'Hepatopulmonary syndrome'

c43185880-01

Proprietary confidential information © 2024 Boehringer Ingelheim International GmbH or one or more of its affiliated companies.

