#### Boehringer Ingelheim BI Trial No.: 1366-0055 c42374778-02 Clinical Trial Protocol

Page 18 of 98

UGT	Uridine Glucuronyl Transferase
ULN	Upper limit of normal
US	Ultrasound
VAS	Visual Analogue Scale
VCTE	Vibration Controlled Transient Elastography
VH	Variceal Haemorrhage
WHO	World Health Organisation
WHVP	Wedged Hepatic Venous Pressure
WOCBP	Woman of childbearing potential

Page 19 of 98

Proprietary confidential information © 2023 Boehringer Ingelheim International GmbH or one or more of its affiliated companies

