#### 2.1.3 Secondary endpoints

Secondary endpoints include:

- occurrence of a response, which is defined as >10% reduction from baseline HVPG (measured in mmHg) after 8 weeks of treatment
- occurrence of further decompensation events (i.e. ascites, VH, and / or overt HE) during the 8-week treatment period
- occurrence of CTCAE grade 3 (or higher) hypotension or syncope based on Investigator judgement, during the 8-week treatment period
- occurrence of discontinuation due to hypotension or syncope during the 8-week treatment period

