#### 3.3.2 Inclusion criteria

- 1. Signed and dated written informed consent in accordance with ICH-GCP and local legislation prior to admission to the trial
- 2. Male or female who is  $\geq 18$  (or who is of legal age in countries where that is greater than 18) and  $\leq 75$  years old at screening (Visit 1a)
- 3. Diagnosis of cirrhosis due to non-cholestatic liver disease (including HCV, HBV, NASH, alcohol-related liver disease, autoimmune hepatitis, Wilson's disease, haemachromatosis, alpha-1 antitrypsin [A1At] deficiency)
- 4. One previous clinically significant decompensation event with clinical resolution at least 4 weeks prior start of screening (visit 1a):
  - a. First variceal haemorrhage
  - b. First episode of clinically significant ascites (requiring intervention in lifestyle [fluid and salt restriction] or medical treatment)
- 5. Willing and able to undergo HVPG measurements per protocol (based on Investigator judgement)
- 6. If receiving statins must be on a stable dose for at least 3 months prior to screening (Visit 1b), with no planned dose change throughout the trial
- 7. If receiving treatment with NSBBs or carvedilol must be on a stable dose for at least 1 month prior to screening (Visit 1b), with no planned dose change throughout the trial
- 8. For patient with alcohol-related cirrhosis, abstinence from significant alcohol misuse / abuse for a minimum of 2 months prior to screening (Visit 1a), and the ability to abstain from alcohol throughout the trial (both evaluated based on Investigator judgement)
- 9. WOCBP must be ready and able to use highly effective methods of birth control per ICH M3 (R2) that result in a low failure rate of less than 1% per year when used consistently and correctly from the randomisation visit (Visit 2) until 7 days after the last treatment in this trial. The patient must agree to periodic pregnancy testing during participation in the trial. Refer to Section 4.2.2.3 and the patient information for a list of contraception methods meeting these criteria
- 10. Men able to father a child and who have a female sexual partner of CBP, must use a condom with or without spermicide, or adopt complete sexual abstinence, or be vasectomised (with appropriate post-vasectomy documentation of the absence of sperm in the ejaculate), from the randomisation visit (Visit 2) until 7 days after the last treatment in this trial. Refer to Section 4.2.2.3 and the patient information for further details

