5.2.2 Secondary endpoint(s)

The secondary endpoints will be used as defined in CTP Section 2.1.3.

c43185880-01

c43185880-01

c43185880-01

Proprietary confidential information © 2024 Boehringer Ingelheim International GmbH or one or more of its affiliated companies.

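### SAP Table 7.5.2:1 has no scope that matches the protocol's variceal haemorrhage component: the narrow list names no gastric site, the broad list is not limited to varices, and neither is named as the endpoint

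*SAP*

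**What the plan says.** Protocol 2.1.3 lists as a secondary endpoint the "occurrence of further decompensation events (i.e. ascites, VH, and / or overt HE) during the 8-week treatment period". The protocol's abbreviation list expands VH as "Variceal Haemorrhage" and adds no site. Inclusion criterion 4 in Protocol 3.3.2 describes one of the two qualifying events in the same open way, as "First variceal haemorrhage".

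SAP 5.2.2 adopts the endpoint without change: "The secondary endpoints will be used as defined in CTP Section 2.1.3". SAP 7.5.2.1 then gives the operational coding in Table 7.5.2:1. For variceal haemorrhage the narrow scope is "PT - 'Oesophageal varices haemorrhage' PT - 'Oesophageal haemorrhage' PT 'Bleeding varicose vein", and the broad scope is "HLT – 'Gastric and oesophageal haemorrhages' HLT – 'Non-site specific gastrointestinal haemorrhages". The same section says that "only descriptive statistics will be presented".

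The endpoint survives the early stop of the programme. SAP Section 4 drops the HVPG analyses, while Table 6.4:1 still assigns liver decompensation to the treated set.

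**The concern.** The endpoint is defined by the origin of the bleed (varices), wherever the varices are. The narrow list is organised mainly by anatomy: two of its three terms name the oesophagus, and none names the stomach. The broad list does reach the stomach, but takes in all bleeds under two HLTs without regard to origin. Neither list reproduces what the protocol says will be counted.

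This could misclassify a true event. VH is one of the decompensation events that end trial treatment under Protocol 3.3.4.1. A participant could stop treatment for a gastric variceal bleed and still not appear under VH in the narrow count. The broad count could pick up that participant, but together with participants whose bleeding had nothing to do with portal hypertension. With the HVPG endpoints gone, decompensation is one of the few secondary endpoints left to report, so its counting rule should be unambiguous.

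**Working it through.** The plan states no figure on this point, so there is nothing to reproduce. The check compares each listed term with the protocol's component, going by the names of the terms alone.

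| Term in Table 7.5.2:1 | Scope | Names a gastric site? | Limited by name to varices? |
|---|---|---|---|
| Oesophageal varices haemorrhage | narrow | no | yes |
| Oesophageal haemorrhage | narrow | no | no |
| Bleeding varicose vein | narrow | no (no site given) | yes |
| Gastric and oesophageal haemorrhages (HLT) | broad | yes | no |
| Non-site specific gastrointestinal haemorrhages (HLT) | broad | no | no |

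- Narrow terms that name a gastric site: 0 of 3.
- Broad terms limited by name to varices: 0 of 2.
- Narrow terms that do not require varices: 1 of 3 (*Oesophageal haemorrhage*).

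Four kinds of report, followed through the table:

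1. An oesophageal variceal bleed, coded as such, is in the narrow count. This agrees with the protocol.
2. A gastric variceal bleed coded to *Bleeding varicose vein* is also in the narrow count. This agrees with the protocol.
3. A gastric variceal bleed coded to a gastric term matches no narrow term. From its name, the HLT "HLT – 'Gastric and oesophageal haemorrhages" would take it into the broad count. The protocol counts this event; the narrow scope does not.
4. An oesophageal bleed without varices, coded to *Oesophageal haemorrhage*, is in the narrow count. The protocol does not count this event; the narrow scope does.

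Cases 3 and 4 show that the narrow scope can err in both directions. The broad scope could repair case 3 only by adding every other bleed that falls under its two HLTs.

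Finally, SAP 7.5.2.1 was read for a rule that selects a scope. It gives none. It does not say which scope is the endpoint, whether the two are shown in separate rows, or whether they are combined.

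**The case against.** The strongest reply has four parts.

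*Coding.* The MedDRA hierarchy is not in the documents, and one narrow term carries no site. A gastric variceal bleed coded to that term would be counted. This stands: the event may be missed, depending on coding. A reader might infer that the narrow scope always misses gastric variceal bleeds, and the documents do not support that. Likewise, the placement of such a bleed under the broad HLT is inferred from the HLT's name.

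*Role of the narrow scope.* The SAP never says that the narrow scope is the endpoint count. A reader might infer that such a participant will be reported as free of decompensation. That would require the narrow scope to be the endpoint, which the text does not say. If both scopes are shown or combined, the event is probably somewhere in the table. This also stands, but it exposes a gap of its own: the SAP leaves the choice open, and the scope that would hold the event is not specific to VH.

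*Other outputs.* The event would appear in the tables by system organ class and preferred term and, where applicable, among AEs leading to discontinuation or serious AEs (SAP 7.8.1.3). It would be expected in the user-defined bleeding category (SAP 7.8.1.5) too. In a small trial a reader could find a single case. None of these outputs labels it as VH or as a decompensation event, so they soften the problem without removing it.

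*Added term alone.* Adding a gastric term would not by itself make the narrow scope equal to VH, because *Oesophageal haemorrhage* does not require varices and varices can be at other sites. This is correct, and the fix covers both.

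**Conclusion.** The mismatch stands as a matter of definition. The protocol counts VH at any site, the SAP says it uses that endpoint, and neither scope in Table 7.5.2:1 returns it. A gastric variceal bleed coded to a gastric term may be left out of the narrow count and appear only in a broad count that also holds non-variceal bleeds. Which of the two is the endpoint is not stated.

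The size cannot be given from the documents. It would need the number of VH events, their split by site, how they were coded and the number treated per arm, and the documents give none of these. A reader might work out that one missed event is 1/20 = 5 percentage points of an arm. That uses the planned 20 per group in Protocol 7.5. SAP Section 4 reports that the programme was discontinued in May 2024 before any participant finished 8 weeks, and does not give the number treated. A reader might also apply a typical gastric share to estimate the proportion of VH missed, but no such share is in the documents.

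The practical weight is small: no hypothesis is tested, the analysis is descriptive and the trial has ended early. The point is worth making because a stated counting rule can misclassify a true event and is nearly free to correct.

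**What to change.** In SAP Table 7.5.2:1 and the text above it:

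1. Add to the narrow scope the preferred term(s) for gastric variceal haemorrhage, and for variceal haemorrhage at any other site, looked up in the MedDRA version in use.
2. State that the narrow scope is the VH component of the decompensation endpoint.
3. Keep the two broad HLTs as a sensitivity row only.
4. Count *Oesophageal haemorrhage* in the narrow scope only when the report confirms varices; otherwise leave it to the sensitivity row.

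The first step must come before any trimming of the table. If the HLTs were deleted without it, bleeds coded to a gastric term would be lost from the table altogether.

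The cost is one added table line and two or three sentences, plus a look at any report coded to *Oesophageal haemorrhage*. No new assessments are needed. The term list and any such review should be settled before treatment codes are released under SAP Section 8. If they have already been released, the change should be reported as made afterwards.

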7.7 EXTENT OF EXPOSURE

A descriptive statistics table with mean, SD, median and range of the number of days a patient was on treatment will be provided for the treated set. The tables will also provide the sum total of the time that all patients pooled together were on treatment. A separate listing will be created for patients who switched treatment, had dose interruption or dose down-titration any time indicating exposure to each treatment.

A frequency table of number and percent of patients belonging to each categorical range of exposure weeks will be provided as well. The following are the categories of exposure-ranges (in weeks):

```
\succ "0 to 4 weeks",
```

```
\blacktriangleright "> 4 to 8 weeks".
```

No temporary treatment interruption (≤ 3 doses) period will be reported.

7.8 SAFETY ANALYSIS

All safety analyses will be performed based on the TS following BI standards. Additionally, AE reported to be related to study procedures will be listed based on the SCR.

7.8.1 Adverse Events

AEs will be coded with the most recent version of MedDRA coding dictionary. Patients will be analyzed according to the actual treatment received.

Any clinically significant new finding in the physical examination, vital signs (blood pressure and pulse symptoms) and in the 12-lead ECG starting after visit 2 (randomisation visit) will be considered as an AE and will be reported as such.

The analyses of AEs will be descriptive in nature. All analyses of AEs will be based on the number of patients with AEs and not on the number of AEs.

7.8.1.1 Assignment of AEs to treatment

In general, the analysis of AEs will be based on the concept of treatment emergent AEs. That means that all AEs occurring between first drug intake till 7 days (residual effect period – REP) after last drug intake will be assigned to the on-treatment period. All AEs occurring before first drug intake will be assigned to 'screening' and all AEs occurring after last drug intake + REP of 7 days will be assigned to 'follow-up' (for listings only). For details on the treatment definition, see Table 6.1:1.

If only the start date of an AE is collected (without the start time), any AE occurrence on the same day as the first Avenciguat administration will be assigned to the on-treatment phase.

In general, in-text AE tables will only present AEs assigned to the first treatment taken except drug-related AEs which will be presented as actual treatment taken at each given timepoint.

Proprietary confidential information © 2024 Boehringer Ingelheim International GmbH or one or more of its affiliated companies.

AEs and serious adverse events (SAEs) assigned to the following phases: screening, each treatment group (placebo, Avenciguat), post-treatment for each treatment group will be listed.

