#### 5.2.6.2 Adverse event collection and reporting

#### 5.2.6.2.1 AE Collection

The investigator shall maintain and keep detailed records of all AEs in the participant files . Per default SAEs/AESIs should be reported via the eCRF in the EDC system. If the EDC system is not or no longer available (e.g. after database lock), the BI paper SAE form should be used; please see Section 5.2.6.2.2. The following must be collected and documented:

- From signing the informed consent onwards until the individual participant's end of trial (= the End of Study [EoS] visit, please see Section 6.2.3): all AEs (serious and non-serious) and all AESIs.
- After the individual participant's end of trial: the investigator does not need to actively monitor the participant for new AEs but should only report any occurrence of cancer of new histology and trial drug related SAEs and trial drug related AESIs of which the investigator may become aware of by any means of communication, e.g. phone call.

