#### 7.2.6 Safety analyses

Adverse events will be coded using the Medical Dictionary for Drug Regulatory Activities (MedDRA). Standard BI summary tables and listings will be produced. All adverse events

with an onset between start of treatment and end of the REP, a period of 7 days after the last dose of trial medication, will be assigned to the on-treatment period for evaluation.

Safety analyses will be done by "treatment at onset" principle. All treated trial participants will be included in the safety analysis. In general, safety analyses will be descriptive in nature and will be based on BI standards. No hypothesis testing is planned.

Statistical analysis and reporting of adverse events will concentrate on treatment-emergent adverse events, i.e. all adverse events occurring between start of treatment and end of the REP. Adverse events that start before first drug intake and deteriorate under treatment will also be considered as 'treatment-emergent'.

Frequency, severity, and causal relationship of adverse events will be tabulated by system organ class and preferred term after coding according to the current version of the Medical Dictionary for Drug Regulatory Activities (MedDRA) at database lock.

Laboratory data will be analysed both quantitatively as well as qualitatively. The latter will be done via comparison of laboratory data to their reference ranges. Values outside the reference range as well as values defined as clinically relevant will be summarised. Treatment groups will be compared descriptively with regard to distribution parameters as well as with regard to frequency and percentage of trial participants with abnormal values or clinically relevant abnormal values.

Vital signs, physical examinations, or other safety-relevant data observed at screening, baseline, during the course of the trial and at the end-of-trial evaluation will be assessed with regard to possible changes compared to findings before start of treatment.

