3. INTRODUCTION

As per ICH E9 (9.1), the purpose of this document is to provide a more technical and detailed elaboration of the principal features of the analysis described in the protocol, and to include detailed procedures for executing the statistical analysis of the primary and secondary variables and other data.

This TSAP assumes familiarity with the Clinical Trial Protocol (CTP), including Protocol Amendments. In particular, the TSAP is based on the planned analysis specification as written in CTP Section 7 "Statistical Methods and Determination of Sample Size". Therefore, TSAP readers may consult the CTP for more background information on the study, e.g., on study objectives, study design and population, treatments, definition of measurements and variables, planning of sample size, randomization.

The statistical analyses will be performed within the validated working environment CARE, including SASTM (current Version 9.4, by , and a number of SASTM-based tools (e.g., macros for the analyses of AE data or laboratory data; Report Appendix Generator system (RAGe) for compilation/formatting of the Clinical Trial Report (CTR) appendices). Pharmacokinetic (PK) parameters will be calculated using WinNonlinTM software (version 8.1,

Proprietary confidential information © 2024 Boehringer Ingelheim International GmbH or one or more of its affiliated companies.

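### The SAP assigns every AE with onset before first intake to screening and omits the protocol's rule that such an AE is treatment-emergent if it deteriorates on treatment

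*SAP*

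**What the plan says.** Protocol 7.2.6 (Safety analyses) sets the on-treatment window for AEs as start of treatment to the end of the seven-day residual effect period. It then adds a second route into the treatment-emergent set: "Adverse events that start before first drug intake and deteriorate under treatment will also be considered as" treatment-emergent.

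SAP 7.8.1.1 (Assignment of AEs to treatment) names the same concept: "In general, the analysis of AEs will be based on the concept of treatment emergent AEs". It then explains the concept by timing alone. The on-treatment period takes "all AEs occurring between first drug intake till 7 days" after last intake, and for earlier onsets the rule is "All AEs occurring before first drug intake will be assigned to" the screening phase. Nothing is said about worsening. Screening AEs are mentioned there only as something to be listed.

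SAP Section 3 states that "the TSAP is based on the planned analysis specification as written in CTP Section 7", which is where the protocol's deterioration rule sits. SAP Section 4 declares two changes to the planned analysis: the HVPG analyses are dropped, and intercurrent events are no longer reported. The definition of treatment-emergent is not among them.

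Protocol 5.2.6.2.1 has all AEs collected "From signing the informed consent onwards until the individual participant's end of trial", so an AE can already be open at first dose.

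**The concern.** The two documents define one central safety concept differently, and the difference is not declared. With the HVPG analyses cancelled, AE tables carry most of what the trial will report by treatment group. A drug can do harm by aggravating an event that was already present as well as by causing a new one, and the protocol's second sentence is there to capture the first kind. The SAP rule, applied literally, removes it for events that began in screening. If one arm aggravates such events more than the other, that arm loses more of them from its tables.

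**Working it through.** No arithmetic applies: the documents give neither a count of AEs open at first dose nor a rate of worsening. The check is to take each kind of event and apply both rules.

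| Event | Protocol 7.2.6 | SAP 7.8.1.1 as written |
|---|---|---|
| A. Onset from first intake to last intake + 7 days | Treatment-emergent | On-treatment |
| B. Onset between consent and first intake, no worsening | Not treatment-emergent | Screening |
| C. Onset between consent and first intake, worsens on treatment, same AE record | Treatment-emergent | Screening |
| D. As C, but the worsening is entered as a new AE | Treatment-emergent | On-treatment, through the new record |
| E. Condition present before inclusion that worsens on treatment | Treatment-emergent, through the recorded worsening | On-treatment, through the recorded worsening |

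Row E rests on Protocol 5.2.6.1.1, which has worsening of the underlying disease or of another pre-existing condition recorded, while abnormalities present before inclusion are held as baseline conditions. The recorded worsening can then carry an on-treatment onset of its own.

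The rules disagree only in row C. The SAP set is the protocol set minus row C, so the discrepancy has one direction.

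Row C can arise. AEs are collected from consent, the Flow Chart has them recorded at both screening visits, the screening period is planned at up to four weeks, and it includes an invasive HVPG measurement.

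The effect on a table is limited by the way AEs are counted. SAP 7.8.1 counts participants with AEs, not AEs. The under-count in a given row is therefore the number of participants whose only qualifying event in that row is of type C. In the table by maximum CTCAE grade, such a participant either disappears or appears at a lower grade because of a milder event. The tables in SAP 7.8.1.3 for serious events, dose reduction and discontinuation would be affected in the same way if they draw on the on-treatment period.

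**The case against.** The strongest reply is that silence is not repeal. The SAP opens the paragraph with a general qualifier, invokes a concept that the protocol defines, and assumes familiarity with the protocol. The protocol too assigns AEs to the on-treatment period by onset first and adds deterioration separately. SAP 7.8 and 7.8.1.3 also defer to sponsor standards on AE analysis, which may contain a worsening rule.

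Part of this stands: the sponsor's programmers may in practice apply the protocol rule, and the documents cannot show that they will not. But the SAP does more than stay silent. It spells out what the concept means by timing and then uses the word all for earlier onsets. The general qualifier is followed by no exception for worsening. The protocol also relies on sponsor standards in 7.2.6 and still found it necessary to state the rule.

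A second reply is that worsening is recorded separately anyway. This stands for conditions present before inclusion (row E). Protocol 5.2.6.1.1 does not say that an AE arising after consent gets a new record when it worsens. If every worsening did open a new record with an on-treatment onset, the protocol's deterioration sentence would have little left to do.

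A third reply concerns importance: all analyses are descriptive (Protocol 7.1), screening AEs remain in listings, and biomarker and PK summaries are still planned, so AE tables are not the only output left. All of that is correct. It limits the consequence without reconciling the two definitions.

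**Conclusion.** The conflict is real and undeclared, and it is narrow. Read as written, the SAP omits from the on-treatment AE tables an AE that starts between consent and first dose and worsens on treatment under the same record. The direction is an under-count only. The size cannot be estimated: no rates are given, the number treated after the programme stop is not stated, and the planned 20 per arm is no longer a safe denominator. The conclusion assumes that the SAP wording is applied literally and that worsening does not always open a new AE record.

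Two stronger readings are tempting. A reader might infer that on-drug worsening in general drops out of the safety tables. Rows D and E show that it does not.

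A reader might also infer that ascites first recorded in screening and worse after first dose is a further decompensation under the protocol and is lost under the SAP. The documents do not say so. Protocol 2.1.3 counts further events during the eight-week treatment period, the deterioration rule sits in the safety section, and SAP 7.5.2.1 supplies MedDRA categories without a rule on onset or worsening. Inclusion criterion 4 asks for one previous decompensation, resolved at least four weeks before screening, and eligibility is reviewed again at Visits 1b and 2, so clinically significant ascites arising in screening would itself raise an eligibility question. What can be said is that neither document settles how a screening-onset event that worsens is handled for this endpoint, or for the hypotension and syncope endpoints.

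This is an alignment correction to a core safety definition, worth making, but not a defect that by itself undermines the report.

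**What to change.** In SAP 7.8.1.1:

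- Restore the protocol rule: an AE with onset before first intake that deteriorates between first intake and last intake + 7 days is assigned to the on-treatment period and counted in the treatment-emergent AE tables.
- State how deterioration is identified and dated, or state that worsening always opens a new AE record. The protocol leaves the term undefined, so a specific trigger such as a rise in CTCAE grade would be the sponsor's choice to make and record.
- State whether such an event counts toward the AE-based secondary endpoints in Protocol 2.1.3: decompensation, grade 3 or higher hypotension or syncope, and discontinuation due to hypotension or syncope.

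If the narrower definition is intended, declare it with a reason in SAP Section 4.

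The cost is a few sentences and, if worsening does not open a new record, one derivation. No new data are needed provided the date of worsening is already captured; the documents do not show the eCRF layout, so that should be confirmed. The wording should be settled before the treatment information is released under SAP Section 8.
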